## 4.7.2 Additional Safety Analyses Performed for COVID-19

Based on the first reports of COVID-19 infection globally, the Sponsor determined that the window for all analyses of COVID-19 associated events would start from 01 December 2019, until CCOD for the study. At the time of the Update CSR, the Sponsor developed a narrow search strategy to identify AEs of confirmed or suspected COVID-19 infection, a Roche Adverse Event Grouped Term (AEGT) that included 19 terms identified by Maintenance and Support Services Organization (MSSO) as relevant to the COVID-19 infection. These AEGT terms were used to assess the impact of COVID-19 in the Update CSR.

Following the MedDRA 23.1 release, a COVID-19 SMQ (narrow) is now available. This SMQ includes 18 terms relevant to COVID-19 infection (see Table 1), and these terms will be used to assess the impact of COVID-19 in the Final CSR. Patients with AEs from this COVID-19 SMQ (narrow) will be considered to have a confirmed or suspected COVID-19 infection.

A listing or table of confirmed and suspected COVID-19 AEs will be produced from the patients identified from the search as having confirmed or suspected COVID-19 infection (Table 1).

Table 1 Roche COVID-19 SMQ (narrow) Preferred Terms for all Cases (Confirmed and Suspected)

Asymptomatic COVID-19

Coronavirus infection

Coronavirus test positive

COVID-19

COVID-19 immunisation

COVID-19 pneumonia

COVID-19 prophylaxis

COVID-19 treatment

Exposure to SARS-CoV-2

Multisystem inflammatory syndrome in children

Occupational exposure to SARS-CoV-2

SARS-CoV-2 antibody test positive

SARS-CoV-2 carrier

SARS-CoV-2 sepsis

SARS-CoV-2 test false negative

SARS-CoV-2 test positive

SARS-CoV-2 viraemia

Suspected COVID-19

In addition to presenting the suspected/confirmed COVID-19 infections, the Sponsor developed a broad search strategy for AEs associated with COVID-19 infection to further evaluate the confirmed events of COVID-19 and reported AEs that could be considered complications of the disease. This search strategy includes both the AEs of a confirmed or suspected COVID-19 infection (PTs in Table 1) and any AEs considered associated with COVID-19 (temporally reported around PTs in Table 2). As causality to COVID-19 was not collected on the standard eCRF, the Sponsor identified associated AEs as those reported ≤7 days before and ≤30 days after any reported AE suggesting a confirmed COVID-19 infection (PTs listed in Table 2). The COVID-19 associated AEs for patients with confirmed COVID-19 infection will be provided in a summary table or a listing.

Table 2 Roche COVID-19 SMQ (narrow) Preferred Terms for Confirmed Cases

Coronavirus Infection

Coronavirus Test Positive

COVID-19

COVID -19 Pneumonia

Sars-Cov-2 Test Positive

SARS-CoV-2 sepsis

SARS-CoV-2 viraemia

**COVID-19 Treatment** 

Multisystem Inflammatory Syndrome in Children

# 4.7.3 Laboratory Data

Laboratory data will be collected at baseline only (see Study GR40548 Protocol Section 4.5.7). These data can be used for interpretation of some AEs, no general summary is planned.

#### 4.7.4 Vital Signs

Vital signs will be collected at screening, randomization and Week 96 or early termination visit only. These data can be used for interpretation of some AEs, no general summary is planned.

# 4.7.5 Ocular Assessments

Results of the following ocular assessments will be summarized by treatment group, by timepoint and by eye (study vs. non-study) as applicable, using descriptive summaries:

- intraocular pressure (IOP)
- slit lamp examination
- indirect ophthalmoscopy

Changes from baseline for IOP assessments will be tabulated. The presence of intraocular inflammation and vitreous hemorrhage, as determined on slit lamp examination, will be tabulated by grade (according to grading scales for flares and cells in Study GR40548 Protocol Appendix 7, and vitreous hemorrhage density and functional scales in Study GR40548 Protocol Appendix 8). The presence of retinal break or detachment as determined from ophthalmoscopy will be tabulated.

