# 5.1.2 Risks Associated with Intravitreal Ranibizumab Injection

# 5.1.2.1 Increased Intraocular Pressure

Transient increases in IOP have been seen within 60 minutes of injection of ranibizumab. Sustained IOP increases have also been reported. Both IOP and perfusion of the optic nerve head must be monitored and managed appropriately.

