# Table 4Dose Interruption, Study Treatment Discontinuation, or Study
Discontinuation Criteria

Event	Dose Interruption Criteria
Intraocular inflammation	Interrupt dose if intraocular inflammation is $\geq 2+$ in the study eye (see the definitions of intraocular inflammation in Section 5.1.2.3). Study treatment may be delayed or the patient may be discontinued from study treatment after consultation with the Medical Monitor.
BCVA decrease	Interrupt dose if there is a study drug–related decrease of $\geq$ 30 letters in BCVA in the study eye compared with the last assessment of BCVA.
Elevated IOP	Interrupt ranibizumab study treatment via intravitreal injection if pre-treatment IOP in the study eye is $\geq$ 30 mmHg. Treatment will be permitted when IOP has been lowered to < 30 mmHg, either spontaneously or by treatment, as determined by the investigator. Note: In the implant arm, if IOP in the study eye is $\geq$ 30 mmHg at an implant refill-exchange visit, study treatment may proceed if the implant is seated in correct position.
Rhegmatogenous retinal break or detachment and macular hole Stages 3 or 4	Interrupt dose if a retinal break is present in the study eye. Treatment may be resumed $\geq 28$ days after the retinal break has been successfully treated. Patients with a rhegmatogenous retinal detachment or Stage 3 or 4 macular holes may require discontinuation from study treatment after consultation with the Medical Monitor.
Local or systemic infection	Interrupt dose if any of the following are present: infectious conjunctivitis, infectious keratitis, infectious scleritis, or endophthalmitis in either eye. Dose should be interrupted if the patient is currently under observation or receiving treatment for a suspected or confirmed severe systemic infection per clinical judgment (including COVID-19).
IV corticosteroids	Dose may be interrupted after consultation with the Medical Monitor if patients need to receive IV corticosteroids. Study treatment may be resumed when the patient has finished IV corticosteroid course.
Intraocular surgery	Dose may be interrupted after consultation with the Medical Monitor if intraocular surgery (except cataract, see Section 4.4.1) has been performed in the study eye within the previous 28 days.

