## 5.2.1 Adverse Events

According to the ICH guideline for Good Clinical Practice, an adverse event is any untoward medical occurrence in a clinical investigation subject administered a pharmaceutical product, regardless of causal attribution. An adverse event can therefore be any of the following:

- Any unfavorable and unintended sign (including an abnormal laboratory finding), symptom, or disease temporally associated with the use of a medicinal product, whether or not considered related to the medicinal product
- Any new disease or exacerbation of an existing disease (a worsening in the character, frequency, or severity of a known condition) (see Sections 5.3.5.8 and 5.3.5.9 for more information)
- Recurrence of an intermittent medical condition (e.g., headache) not present at baseline
- Any deterioration in a laboratory value or other clinical test (e.g., ECG, X-ray) that is associated with symptoms or leads to a change in study treatment or concomitant treatment or discontinuation from study drug
- Adverse events that are related to a protocol-mandated intervention, including those that occur prior to assignment of study treatment (e.g., screening invasive procedures such as biopsies)

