#### 4. STATISTICAL METHODS

Descriptive summaries will include the mean, standard deviation, median, and range for continuous variables, and counts and percentages for categorical variables.

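### The SAP summarises intraocular pressure by visit but never counts patients with raised pressure, and adverse event counts are not a reliable substitute.

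*SAP*

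**What the plan says.** SAP 4.7.5 lists IOP first among three ocular assessments: "Results of the following ocular assessments will be summarized by treatment group, by timepoint and by eye" (study versus non-study). SAP Section 4 defines the content: "Descriptive summaries will include the mean, standard deviation, median, and range for continuous variables". SAP 4.7.5 then adds: "Changes from baseline for IOP assessments will be tabulated". Protocol 6.5.2 has a similar plan. Neither section contains a threshold, category, worst-value or consecutive-visit summary of IOP. Other findings in SAP 4.7.5 are treated differently: "The presence of intraocular inflammation and vitreous hemorrhage, as determined on slit lamp examination, will be tabulated by grade", and retinal break or detachment is tabulated as present or absent.

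Protocol 5.1.2.1 names the risk under intravitreal ranibizumab: "Sustained IOP increases have also been reported". Protocol 5.1 lists transient and sustained IOP elevation among the issues tied to ranibizumab or its route of administration. Protocol 5.1.4.1 says that a sustained rise can be associated with glaucoma and so with permanent vision loss, while noting no conclusive evidence to date that the reported rises develop into glaucoma. Increased IOP is not on the ocular list of adverse events of special interest (Protocol 5.2.3, SAP 4.7.1).

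Table 4 in Protocol 5.1.5.2 gives the dosing rule: "Interrupt ranibizumab study treatment via intravitreal injection if pre-treatment IOP in the study eye is" 30 mmHg or more. For an implant refill-exchange at that same pressure, "study treatment may proceed if the implant is seated in correct position". Under Protocol 5.2.1, a deterioration in a clinical test is an AE if it comes with symptoms or "leads to a change in study treatment or concomitant treatment or discontinuation from study drug".

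**The concern.** Raised IOP is a matter of individual eyes. What a safety reader needs is how many patients in each arm reached a high pressure, and in how many it lasted. A by-visit summary answers neither. The mean moves little when a few eyes rise. The range gives one extreme value per visit but not the number of patients behind it. And because each visit is summarised separately, no output links one visit to the next in the same eye, so a sustained rise cannot be told apart from different eyes being high at different visits.

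The natural fallback is the AE tables. Their input differs by arm, because the same reading changes study treatment at an intravitreal injection visit and need not do so at a refill visit. At stake is a between-arm comparison of a named risk that would rest on summaries that hide the count and on AE reports whose trigger is not the same in both arms.

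**Working it through.** The documents give no IOP event rate or standard deviation, so there is no plan figure to reproduce. The check is a visit count, a reading of two rules side by side, and one illustration on assumed inputs.

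**Visits after Day 1** (Protocol Appendices 1 and 2; supplemental visits from Protocol 5.1.5.3)

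- Intravitreal arm, IOP visits: Weeks 4 to 96 every 4 weeks = (96 − 4)/4 + 1 = 24.
- Intravitreal arm, injection visits: Weeks 4 to 92 = (92 − 4)/4 + 1 = 23.
- Implant arm, IOP visits: the same 24 plus Days 2 and 7 = 26.
- Implant arm, refill-exchange visits: Weeks 24, 48 and 72 = 3.
- Implant arm, possible supplemental injections: Weeks 16, 20, 40, 44, 64, 68, 88 and 92 = 8, each only if the supplemental criteria are met.
- Visits common to both arms: 24 over the study, and 10 through Week 40 (40/4).

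**The two rules side by side**, for a pre-treatment study-eye reading of 30 mmHg or more without symptoms and without IOP-lowering treatment

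- At an intravitreal injection visit, Table 4 requires interruption. Study treatment changes, so the treatment-change criterion in Protocol 5.2.1 is met.
- At a refill visit, treatment may proceed if the implant is correctly seated. Study treatment need not change, so the criterion need not be met.
- At the remaining implant-arm visits no study treatment is scheduled, apart from a possible supplemental injection.
- If the patient has symptoms or is given IOP-lowering treatment (permitted by Protocol 4.4.1), an AE criterion is met in either arm.

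The asymmetry is thus confined to asymptomatic, untreated readings.

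**How little the mean moves (assumed inputs)**

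Suppose a share p of one arm rises by r mmHg at a visit; the arm mean shifts by p × r.

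| p | r = 10 | r = 15 |
|---|---|---|
| 1% | 0.10 | 0.15 |
| 2% | 0.20 | 0.30 |
| 5% | 0.50 | 0.75 |

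The 418 enrolled patients split 3:2 give about 251 and 167. The 95% half-width of the difference in mean change is 1.96 × SD × √(1/251 + 1/167): 0.59 mmHg for an assumed SD of 3, and 0.78 mmHg for an assumed SD of 4. Most of these shifts are smaller than 0.59, and all are smaller than 0.78. No IOP test is planned, so this shows only how weakly the mean reflects a few high eyes; it does not predict a result.

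**The case against.** A reader who sees only the sentence on change from baseline might infer that IOP is reported in no other way. The documents do not support that. The preceding text plans by-visit summaries of IOP itself, and the range shows each visit's lowest and highest value. The standard deviation would react too: with 5% of eyes at +15 mmHg and a base SD of 3, it becomes √(9 + 225 × 0.05 × 0.95) = 4.4. An extreme eye would therefore be visible. What remains missing is the number of patients and the link between visits.

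A reader might also infer that the arm comparison of IOP would be wrong, with AE counts biased against the intravitreal arm. That is not shown. Treatment change is one AE criterion among several; Protocol 5.2.1 also covers any unfavourable and unintended sign, which applies equally in both arms. Protocol 5.1.5.2 asks for an AE form entry on interruption only where applicable. A rise that is treated qualifies as an AE in both arms. The documents support a difference in one trigger, not a bias of known size.

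Three further points are fair. Protocol 5.1.2.1 places the IOP risk under intravitreal injection, and the implant risks in 5.1.3 do not list it. The figure of 30 mmHg is a dosing trigger, not a declared safety endpoint. And part of what a reader needs is already planned: ocular concomitant medications for the study eye (SAP 4.2) and ocular AEs in the study eye, also split at 37 days (SAP 4.7.1). None of these outputs gives a measured count of patients with high pressure.

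**Conclusion.** The concern holds as a gap in the planned outputs. SAP 4.7.5 describes IOP at each visit but has no patient-level count of raised or sustained IOP, and AE counts cannot be relied on to supply it, because one AE trigger differs by arm. The exposure to that trigger is 23 injection visits after Day 1 against 3 refill visits where treatment may proceed, with up to 8 conditional supplemental visits.

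The size of any distortion in AE counts cannot be computed from the documents. It depends on how often asymptomatic, untreated readings of 30 mmHg or more occur and on how investigators report them. The dilution figures rest on assumed rates, rises and SDs. The primary endpoint and its analysis are untouched. Nothing here says that the Table 4 rule should differ; the point concerns only what is counted. This is a cheap improvement.

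**What to change.** Add one table to SAP 4.7.5, by arm and by eye, giving the number and percent of patients with pre-treatment IOP of 30 mmHg or more:

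- at any scheduled post-baseline visit common to both arms (Weeks 4 to 96; Weeks 4 to 40 for the primary analysis period);
- at two or more consecutive such visits.

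Show implant-arm Days 2 and 7 separately, since the intravitreal arm has no matching visits. Use 30 mmHg only as a reporting category, because it already stands in Table 4. Uncontrolled ocular hypertension or glaucoma, including IOP above 25 mmHg despite medication, is an exclusion (Protocol 4.1.2.3), so a study-eye reading of 30 or more would generally be new.

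The data exist: Protocol 4.5.5 requires IOP before treatment at each visit, with the same method for a given patient at office visits. The cost is one extra descriptive table, with no new data and no change to any clinical rule. The table will not capture transient rises soon after an injection, because the scheduled readings precede treatment.

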# 4.7.6 Immunogenicity Analyses

Because patients will have been exposed to ranibizumab prior to entry into study, the ADA status of patients at the randomization visit may not reflect pretreatment ADA prevalence in the study. Thus, the ADA incidence will be analyzed.

The immunogenicity analyses will group patients according to treatment received.

Anti-drug antibody samples will be collected prior to dosing during the randomization

visit and at Weeks 4, 24, 36, and 96. To account for pre-study exposure to ranibizumab, ADA incidence (number and percentage) will be summarized as follows:

- ADA incidence at the time of entry into the study (randomization visit) based on the Safety Population
- ADA incidence at any time after randomization visit, grouped in the following manner, based on patients in the Safety Population who have ADA samples at randomization and after dosing:
  - a) Patients who were ADA negative at randomization and became positive only after dosing, during the study.
  - b) Patients who were ADA positive at randomization and ADA titer increased after dosing during the study; in this case, the titer of one or more samples collected after randomization must be at least 4-fold greater (i.e., > 0.60 titer units) than the titer of the randomization visit sample. These patients are considered to have treatment-enhanced ADA responses.
  - c) Patients who were ADA positive at randomization and ADA titer did not increase after dosing during the study.

The combined rates described in (a) and (b) above will provide the incidence of treatment-emergent ADAs in the study. Patients are considered to be negative for ADAs if they are ADA negative at all timepoints. Patients are also considered to be negative for ADAs if they are ADA positive at randomization and ADA negative at all post-randomization timepoints. A listing of patients with positive serum antibodies to ranibizumab will be provided.

The immunogenicity assessment will also include testing for the presence of neutralizing antibodies in samples confirmed to be positive for anti-ranibizumab antibodies. The incidence of neutralizing antibodies will be grouped and reported in a similar fashion to that described above.

In addition, subgroup analyses will be performed summarizing ADA and neutralizing antibody incidences based on pre-screening anti-VEGF intravitreal treatment.

The relationship between ADA status and safety, efficacy, PK, and biomarker endpoints may be explored.

#### 4.8 MISSING DATA

In efficacy analyses, the handling of missing data is specified for analysis in the efficacy analysis section.

#### 4.9 INTERIM ANALYSES

No interim efficacy or futility analyses are planned. The iDMC will review the interim safety analyses approximately every 6 months

# **Appendix 1 Protocol Synopsis**

TITLE: A PHASE III, MULTICENTER, RANDOMIZED, VISUAL

ASSESSOR-MASKED, ACTIVE-COMPARATOR STUDY OF THE EFFICACY, SAFETY, AND PHARMACOKINETICS OF THE PORT DELIVERY SYSTEM WITH RANIBIZUMAB IN PATIENTS WITH NEOVASCULAR AGE-RELATED MACULAR DEGENERATION

(ARCHWAY)

PROTOCOL NUMBER: GR40548

**VERSION NUMBER:** 5

**EUDRACT NUMBER:** Not applicable

**IND NUMBER:** 113,552

NCT NUMBER: NCT03677934

**TEST PRODUCT:** Port Delivery System with ranibizumab

PHASE: Phase III

**INDICATION:** Neovascular age-related macular degeneration

**SPONSOR:** F. Hoffmann-La Roche Ltd

#### **Objectives and Endpoints**

This study will evaluate the efficacy, safety, and pharmacokinetics of ranibizumab delivered via the Port Delivery System with ranibizumab (PDS) implant compared with ranibizumab 0.5 mg delivered as a monthly intravitreal injection in patients with neovascular age-related macular degeneration (nAMD). Specific objectives and corresponding endpoints for the study are outlined below.

Primary Efficacy Objective	Corresponding Endpoint
To evaluate the non-inferiority and equivalence in efficacy of ranibizumab delivered via the PDS Q24W with the 100-mg/mL formulation compared with that of 10-mg/mL (0.5-mg dose) Q4W intravitreal ranibizumab injections	Change from baseline in BCVA score at the average of Week 36 and Week 40, as assessed using the ETDRS visual acuity chart at a starting distance of 4 meters

Secondary Efficacy Objectives	Corresponding Endpoints
To evaluate the relative efficacy of ranibizumab delivered via the PDS Q24W	Change from baseline in BCVA score averaged over Week     60 and Week 64
with the 100-mg/mL formulation compared	Change from baseline in BCVA score over time
with that of 10-mg/mL (0.5-mg dose) Q4W intravitreal ranibizumab injections, as assessed by visual acuity	
 
Proportion of patients with BCVA score of 38 letters (20/200 approximate Snellen equivalent) or worse at the average over Week 36 and Week 40
 

	
 
Proportion of patients with BCVA score of 38 letters (20/200 approximate Snellen equivalent) or worse over time
 

	
 
Proportion of patients with BCVA score of 69 letters (20/40 approximate Snellen equivalent) or better at the average over Week 36 and Week 40
 

	
 
Proportion of patients with BCVA score of 69 letters (20/40 approximate Snellen equivalent) or better over time
 

	
 
Proportion of patients who lose < 10 or < 5 letters in BOA score from baseline to the average over Week 36 and Week 40
 

	
 
Proportion of patients who lose < 10 or < 5 letters in BO/A score from baseline over time
 

	
 
Proportion of patients who gain ≥0 letters in BCVA score from baseline to the average over Week 36 and Week 40
 

	
 
Proportion of patients who gain ≥0 letters in BCVA score from baseline over time
 

To evaluate the relative efficacy of	Change from baseline in CPT at Week 36
ranibizumab delivered via the PDS Q24W with the 100-mg/mL formulation compared with that of 10-mg/mL (0.5-mg dose) Q4W intravitreal ranibizumab injections, as assessed by CPT on SD-OCT	Change from baseline in CPT over time
To evaluate the proportion of patients who undergo supplemental treatment with intravitreal ranibizumab 0.5 mg	Proportion of patients in the implant arm who undergo supplemental treatment with intravitreal ranibizumab 0.5 mg before the first, second, third, and fourth fixed refillexchange intervals
	Proportion of patients in the implant arm that undergo a supplemental treatment that requires subsequent additional supplemental treatments during the study
Exploratory Efficacy Objectives	Corresponding Endpoints
To evaluate the impact of supplemental treatment with intravitreal ranibizumab 0.5 mg	Endpoints will be results-dependent based on number of supplemental treatment

Exploratory Efficacy Objectives (cont.)	Corresponding Endpoints (cont.)
To evaluate the relative efficacy of ranibizumab delivered via the PDS Q24W with the 100-mg/mL formulation compared with that of 10-mg/mL (0.5-mg dose) Q4W intravitreal ranibizumab injections, as assessed by central subfield thickness on SD-OCT	Change from baseline in CST at Week 36     Change from baseline in CST over time
To assess clinically relevant features using advanced analytics tools (including artificial intelligence-based tools) on multimodal images and clinical data	Clinically relevant features over time
To evaluate the development of macular atrophy in patients treated with the PDS Q24W with the 100-mg/mL formulation compared with those with 10-mg/mL (0.5-mg dose) Q4W intravitreal ranibizumab injections.	
 
Proportion of patients with macular atrophy at baseline, Weeks 36, 48, and 96
 
Change from baseline in macular atrophy area at Weeks 36, 48 and 96
 

To evaluate the relative efficacy of ranibizumab delivered via the PDS Q24W with the 100-mg/mL formulation compared with that of 10-mg/mL (0.5-mg dose) Q4W intravitreal ranibizumab injections, as assessed by visual acuity	
 
Proportion of patients who gain ≥5 letters in BCVA score from baseline over time.
 

Safety Objective	Corresponding Endpoints
To evaluate the safety and tolerability of ranibizumab, delivered via the PDS Q24W with the 100-mg/mL formulation compared with that of 10-mg/mL (0.5-mg dose) Q4W intravitreal ranibizumab injections	
 
Incidence and severity of ocular and systemic (non-ocular) AEs
 
Incidence, severity, and duration of AESIs, including PDS-associated AEs
 
Incidence, severity, and duration of ocular AESIs during the postoperative period (up to 37 days of initial implantation) and follow-up period (>37 days after implantation surgery)
 

Pharmacokinetic Objective	Corresponding Endpoints
To characterize the serum pharmacokinetics of ranibizumab in patients after the initial fill and subsequent refill-exchanges in patients with the PDS	
 
Observed serum ranibizumab concentrations at specified timepoints
 
Additional estimated PK parameter values, including AUC0-6M, Cmax, Cmin, and t1/2 after PDS implant insertion
 

Exploratory Pharmacokinetic Objectives	Corresponding Endpoints
To evaluate potential relationships between drug exposure and the efficacy of the PDS	Relationship between serum concentration or PK parameters for ranibizumab delivered via the PDS and efficacy endpoints

Immunogenicity Objective	Corresponding Endpoint
To investigate the formation of serum anti- ranibizumab antibodies	The incidence of ADAs during the study, grouped in the following manner:
	Patients who were ADA negative at baseline and became positive only after dosing
	Patients who were ADA positive at randomization and ADA titer increased after dosing
	Patients who were ADA positive at randomization and ADA titer did not increase after dosing
Exploratory Biomarker Objectives	Corresponding Endpoints
To explore relationships between aqueous humor free-VEGF concentrations over time and the efficacy of ranibizumab,	Comparison of patients with and without aqueous humor free-VEGF present between refill-exchanges and needing supplemental treatment
delivered via the PDS Q24W with the 100-mg/mL formulation	Comparison of patients with and without aqueous humor free-VEGF present between refill-exchanges and CST change from baseline over time
	Comparison of patients with and without aqueous humor free-VEGF present between refill-exchanges and BCVA score change from baseline over time
To identify biomarkers that are prognostic of response to ranibizumab, are associated with acquired resistance to ranibizumab, are	Relationship between biomarkers in blood and aqueous humor with disease characteristics and response to ranibizumab
associated with susceptibility to developing adverse events (i.e., safety biomarkers), can provide evidence of ranibizumab activity (i.e., pharmacodynamic biomarkers), or can increase the knowledge and understanding	
 
Relationship between genetic variants (such as AMD risk alleles, polymorphisms within the complement pathway, and polymorphisms within the VEGF-A genetic locus) with the disease characteristics and/or response to treatment with ranibizumab
 

of AMD-related disease biology	Relationship between imaging features with disease characteristics and/or response to treatment with ranibizumab
Exploratory Patient Experience Objectives	Corresponding Endpoints
To evaluate the preference of patients for ranibizumab delivered via the PDS for 40 weeks compared to intravitreal anti-VEGF treatment received in the 6 months prior to Day 1	Proportion of patients who report preferring ranibizumab treatment via the PDS compared with intravitreal anti- VEGF treatment, as assessed by the PPPQ, at Week 40 among patients in the implant arm
To evaluate patient-reported treatment satisfaction with ranibizumab delivered via the PDS for 40 weeks compared with that of Q4W intravitreal ranibizumab injections, as assessed by the MacTSQ	MacTSQ total score at Week 40

ADA = anti-drug antibody; AE = adverse event; AESI = adverse event of special interest; AMD = age-related macular degeneration;  $AUC_{0-6M}$  = area under the concentration—time curve from 0 to 6 months;

BCVA = best-corrected visual acuity;  $C_{max}$  = maximum serum concentration;  $C_{min}$  = minimum serum concentration; CPT = center point thickness; CST = central subfield thickness; ETDRS = Early TreatmentDiabetic Retinopathy Study; MacTSQ = Macular Degeneration Treatment Satisfaction Questionnaire; PDS = Port Delivery System with ranibizumab; PK = pharmacokinetic; PPPQ = PDS Patient Preference Questionnaire; Q4W = every 4 weeks; Q24W = every 24 weeks; SD-OCT = spectral domain optical coherence tomography;  $t_{1/2}$  = half-life; VEGF = vascular endothelial growth factor.

